12.12.1 Medically Necessary MRI Visit Source Data Requirements

Source data Requirements for medically necessary MR scans are described in Table 12-11:

Table 12-11: Medically Necessary MRI Visit Source Documentation Requirements

Source Documentation Requirement	Disposition
Pre-MR scan: 
 • Body Part scanned • Assessment of patient history of unexplained syncope • Device Evaluation (pace threshold, sense amplitude, impedance, RV shock impedance, LV Phrenic Stimulation threshold) • PRM ECG strips from manual threshold tests documenting LOC for all implanted leads • Assessment of Beeper function • Printout of ‘Quick Notes’ Report • Cardiology and Radiology MRI Conditions of Use are satisfied • 12 leads ECG & 10s rhythm strip (either from the ECG machine or the BSC PRM) 	Retain at center
While PG is programmed to MRI Protection Mode: 
 • MRI Protection Settings Report • Time of MR scan initiation • Time of MR scan completion • Heart rate, blood pressure, Oxygen saturation levels, and Voice Contact in 5 ± 2 minute intervals • Medications used for sedation in the MR scanner, if applicable • MR Scanner manufacturer and model 	Retain at center
When PG is programmed out of MRI Protection Mode: 
 • Time of exiting MRI Protection Mode 	Retain at center
Post-MR scan: 
 • Device Evaluation (pace threshold, sense amplitude, impedance, RV shock impedance, LV Phrenic Stimulation threshold) • PRM ECG strips from manual threshold tests documenting LOC for all implanted leads • Assessment of Beeper function • Document if polymorphic or monomorphic VT/VF episodes requiring therapy, are present • Documentation of spontaneous VT/VF episode(s) by PRM strips, as applicable: 
 ○ ‘Selected Episodes Report’ (counters and EGMs required) ○ ‘Arrhythmia Logbook’ • Printout of ‘Quick Notes’ Report 	Retain at center
Adverse Events	Retain at center

MR scanner DICOM dump/ report file including items such as scan sequence settings and durations as well as calculated scan metrics such as whole body average SAR. The DICOM file must contain both images and scan sequence data.	Retain the original at the center and submit a copy to Boston Scientific
Save All	Retain the original at the center and submit a copy to Boston Scientific

Text in table that is italicized is recommended

12.13 Study Completion

Subjects will be followed until completion of the 3-year annual follow-up visit. In the US, if a subject receives an investigational lead(s) that is not approved by the FDA before the 3-year annual follow-up, then the subject will be followed until the investigation lead(s) is approved, explanted, or until study closure. Upon completion of participation in the study, subjects will be followed per normal standard of care.

13. Statistical Considerations

13.1 Endpoints (Phase I only)

All Phase I subjects who consent to be part of the VF Sub-study or require a “for-cause” VF induction will contribute to the ancillary analysis of VT/VF assessment.

13.1.1 Primary Safety Endpoint: MR Scan-Related ImageReady System Complication Free Rate

The primary safety endpoint will be assessed for all subjects who undergo any portion of the study-required MR scan sequences. Safety will be confirmed by evaluating the **MR scan-related ImageReady System** Complication-free rate (CFR) between the MR Scan and the MRI Visit + 1 Month. For the purpose of this endpoint, a MR scan-related ImageReady System complication will be defined as those complications that are related to the MR scan and ImageReady System. All complications that the site reports as related to the MR scan and ImageReady System will be adjudicated by an external committee for relation to the MR scan. Complications that are determined to be associated with the MR scan will be considered MR scan-related complications and count against this endpoint.

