21.3 Unanticipated Adverse Device Effects

All devices are subject to occasional random problems or failures. These may manifest themselves in altered pacing or sensing characteristics. There are wide variations in the seriousness of the effects. Refer to the device(s) Physician's Manual for information regarding potential adverse effects.

If the unanticipated adverse device effect is serious or life-threatening, the Investigator is required to notify Boston Scientific, the IRB, and other regulatory authorities as required (e.g., Competent Authority if European center) as soon as possible, but no later than one business day after the Investigator first learns of the effect. For all other unanticipated adverse device effects, Boston Scientific and the IRB must be notified within ten business days.

Boston Scientific will conduct an evaluation of all reported adverse events. If the event is determined to be an unanticipated adverse device effect, Boston Scientific personnel shall notify the Boston Scientific Regulatory department and initiate communication to all reviewing IRBs and participating Investigators within ten business days after initial notice is received.

If Boston Scientific determines that an unanticipated adverse device effect presents an unreasonable risk to patients, the study shall be terminated. The termination shall occur no

later than five days after the termination decision is made and no later than 15 business days after Boston Scientific first received notice of the effect.

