21.4.2 Adverse Event Type Classification

An Investigator is required to report all reportable events (as defined in Section 21.1) for this study. All adverse events must be recorded in the Adverse Event case report form in the EDC system, including an event description, suspected cause, corrective action, and clinical outcome for the patient.

Upon receipt of adverse event information, CRFs are reviewed by BSC personnel or trained authorized personnel. During the review process, the adverse event is classified as an observation or complication and each event is coded according to the types below.

Classifications and type descriptions will be included with the adverse event information in appropriate submissions to the regulatory agencies. If the opinions between the investigator and BSC differ, both opinions will be reported, as appropriate.

Table 21-3: Adverse Event Types I-V Utilized for BSC AE Classification

Type	Description
Type I	Related to an investigational device, investigational procedure, investigational therapy, or procedure related to the implant of the investigational device.
Type II	Related to the protocol or procedures specifically related to protocol testing that is not standard of care.
Type III	Related to commercially available implanted components or commercially available features of an investigational device, or the procedure of a commercially available device
Type IV	Related to a change in the patient's condition or to therapies other than delivered by the implanted system.
Type V	Comments Only

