23.1 Clinical Events Committee

A CEC is an independent group of individuals with pertinent expertise that reviews and adjudicates all of the following, as reported by study investigators for Phase I and II subjects:

- Events related to the study-required MR scan and ImageReady System between the MRI Visit and MRI + 1 month Visit (safety endpoint)
- Events related to medically necessary scan(s) and ImageReady System
- Subject deaths

The CEC will review a safety event dossier, which may include copies of subject source documents provided by study sites. At the discretion of the sponsor, additional events may be sent to the CEC.

Committee members will include a minimum of three practitioners with training in Electrophysiology (EP), and/ or Cardiology with the necessary therapeutic and subject matter expertise to adjudicate the event categories outlined above. CEC responsibilities, qualifications, membership, and committee procedures are outlined in the CEC charter.

24. Suspension or Termination

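### Independent adjudication of a non-fatal complication is mandatory only if the site called it scan- and system-related, so under-attribution by sites is not independently corrected

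*Combined protocol and SAP*

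**What the plan says.** Section 13.1.1 defines the endpoint by complications related to both the MR scan and the ImageReady System. It then says who reviews what: "All complications that the site reports as related to the MR scan and ImageReady System will be adjudicated by an external committee". The committee judges relation to the MR scan, and "Complications that are determined to be associated with the MR scan will be considered MR scan-related complications and count against this endpoint".

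Section 23.1 says the Clinical Events Committee (CEC) "reviews and adjudicates all of the following, as reported by study investigators for Phase I and II subjects". The list has three items: events related to the study scan and system in the endpoint window, events related to medically necessary scans and the system, and deaths. Section 21.5 repeats that deaths must be reviewed. For anything else, "At the discretion of the sponsor, additional events may be sent to the CEC". No referral criteria are given, but "CEC responsibilities, qualifications, membership, and committee procedures are outlined in the CEC charter".

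The sponsor's review is wider. Section 21.3 says "Boston Scientific will conduct an evaluation of all reported adverse events". Under section 21.4.2, sponsor or authorised staff review each report, and "the adverse event is classified as an observation or complication and each event is coded according to the types below". If the sponsor and the investigator disagree, both opinions are reported as appropriate. Referral to the committee is not required.

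Section 13.4.1 presents the committee's determination of endpoint events as the control for variability between observers at different sites.

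**The concern.** Attribution is a real judgement in this study. Section 20.4 lists arrhythmia induction, bradycardia, syncope and worsening heart failure among the possible effects of a scan within the Conditions of Use. Sections 20.1 and 20.2 list the same or similar events as risks of any CRT-D or ICD implant. Two sites could reasonably attribute the same event differently.

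If a site over-attributes, the committee must look and can overrule it. If a site under-attributes a non-fatal event, nothing in the protocol requires the committee to see it. In an unblinded single-arm study tested against a fixed 90% goal, that asymmetry can move the complication-free rate in one direction only: up. The estimate then depends partly on site attribution and sponsor discretion, which falls short of the purpose given in section 13.4.1.

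**Working it through.** **Routes to the committee for an event between the scan and the MRI + 1 Month Visit**

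| Event | Route | Mandatory? |
|---|---|---|
| Death, any attribution | 21.5, 23.1 | Yes |
| Non-fatal complication, site says related to scan and system | 13.1.1, 23.1 | Yes |
| Non-fatal complication, site says unrelated to either | 23.1, sponsor referral | No, discretionary |

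The third row is the gap. Sponsor evaluation (21.3, 21.4.2) covers these events but is not independent and triggers no referral.

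**Size.** The plan gives no figure to reproduce: the safety sample size and expected rate are blacked out, and no miss rate is stated. Inputs:
- Goal of 90% (13.1.1.1) and significance level of 2.5% (13.4.2), taken as one-sided.
- Assumed: N = 200 or 300.
- Assumed: share u of truly related complications missed = 10% to 30%, net of deaths and sponsor referrals. If u is not net of these, the results are upper bounds.
- An exact binomial test stands in for the Kaplan-Meier analysis. The committee is assumed to judge correctly whatever it sees.

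With true event rate p, the observable rate is p(1 − u), so the overstatement of the complication-free rate is p × u:
- p = 1%: 0.1 to 0.3 points.
- p = 2%: 0.2 to 0.6 points. At u = 30% the study would report 98.6% instead of 98.0%. At N = 200 that is 1.2 of 4 expected events missed, and at N = 300 it is 1.8 of 6.
- p = 3%: 0.3 to 0.9 points.

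Pass rule: the largest c with P(X ≤ c | N, 0.10) ≤ 0.025. This gives c = 11 at N = 200 (probability 0.0168) and c = 19 at N = 300 (0.0171). Chance of passing = P(X ≤ c | N, p(1 − u)):

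| True rate p | N = 200, u = 0 | N = 200, u = 30% | N = 300, u = 0 | N = 300, u = 30% |
|---|---|---|---|---|
| 2% | 99.92% | 100.00% | 100.00% | 100.00% |
| 3% | 98.16% | 99.88% | 99.91% | 100.00% |
| 5% | 69.98% | 94.98% | 88.10% | 99.50% |
| 10% (illustration) | 1.68% | 25.08% | 1.71% | 37.82% |

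At p = 1% every entry rounds to 100%. With u = 30%, the chance of passing rises by 5 points or more only from p of about 3.5% (N = 200) or 4.5% (N = 300). The device still truly meets the goal at those rates, so a pass there is not a false one. A false pass needs p of 10% or more.

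**What the cited series say about p.** The largest series in section 4 reports none of its listed outcomes in 829 cases, but 617 of these were pacemakers. For the 212 ICD cases alone, the one-sided 95% upper limit for zero events is 1 − 0.05^(1/212) = 1.4%. Those scans were non-thoracic, whereas this study centres the RF-intensive sequences on the thoracic spine (28.3). The listed outcomes are also narrower than the definition of a complication in 21.4.1. The series is therefore only loose support for a low rate.

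**The case against.** The case on the other side has five parts.

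- **Safeguards.** Serious, cardiac, device-related and scan-related events are all reportable (21.1). Section 21.7 classes weak relationships that cannot be excluded, and unassessable cases, as possibly related. The sponsor reviews every report. This stands as mitigation: sites may miss few events. But 21.7 is worded for the device or procedure rather than the scan, and the protocol does not say which level of relatedness opens adjudication.
- **The charter.** Referral criteria would normally sit there. This stands as a limit: the gap is shown only for the protocol text.
- **Section 13.4.1.** It says the committee determines the endpoint events and states no site filter. In section 23.1, the mention of investigators may simply name the source of reports. That is a possible reading, but section 13.1.1 remains explicit.
- **Consequence.** At plausible rates the pass/fail result does not change. This stands, and it makes the fix a cheap improvement.
- **Scope of the committee's ruling.** Section 13.1.1 asks it to judge relation to the scan only. Letting it also rule on relation to the system would add a ground for removing events. This stands, and the fix respects it.

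A reader might infer that site-missed events can never enter the endpoint, or that the study is likely to pass falsely. The documents support neither. Deaths and referred events can be added, since sections 13.1.1 and 13.4.1 read most naturally as counting whatever the committee finds scan-related. A false pass would need a true rate of at least 10%, which the cited series do not suggest.

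**Conclusion.** The concern holds on the protocol text. Mandatory independent adjudication of non-fatal complications corrects over-attribution by sites but not under-attribution, and any residual error favours the device. The documents do not show that sites will under-attribute; if they miss nothing, there is no bias.

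At a true rate of 1% to 2% and an assumed net miss share of 10% to 30%, the overstatement is 0.1 to 0.6 points and the chance of passing stays at 99.9% to 100%. These figures rest on assumed values of N and the miss share and on a binomial proxy. The 10% row is an illustration only. What is at stake is the credibility of the primary safety estimate rather than the decision. Confidence is medium because the charter was not available. The change is worth making because it is cheap.

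**What to change.** In sections 13.1.1 and 23.1, and in the charter if it does not already say so:

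1. Send to the committee every event classed as a complication under 21.4.1, with onset between the study scan and the MRI + 1 Month Visit, whatever the site's attribution. Apply this to Phase I subjects included in the safety endpoint: scan sequence initiated, and no medically necessary scan in the period excluded by 13.1.1.3.
2. State that the committee's decision on relation to the MR scan, as in 13.1.1, determines whether the event counts, in both directions and including deaths and sponsor-referred events.
3. Do not add relation to the system as a ground for removal unless sections 13.1.1 and 13.4.1 are first reconciled on what the committee decides.

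The cost is wording plus extra dossiers. The committee exists, the window is about one month, and the sponsor already classes every reported event. Some dossiers will concern events unlikely to be scan-related, because 21.4.1 counts treatments such as intravenous medication and transfusion as invasive intervention. The number cannot be told from the documents. Subjects already scanned under earlier protocol versions (11.1.1) would need retrospective review, and the reported rate may be slightly less favourable. If the charter already requires this referral, one confirming sentence in the protocol is enough for step 1.

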13.1.1.1 Hypotheses

The following hypotheses will be used to evaluate the Primary Safety Endpoint:

H_0 : The MR Scan-related CFR rate between MR Scan and MRI Visit + 1 Month \leq 90%

H_A : The MR Scan-related CFR rate between MR Scan and MRI Visit + 1 Month $>$ 90%.

13.1.1.2 Sample Size

[REDACTED]

13.1.1.3 Statistical Methods

Endpoint analysis will be performed on all subjects that undergo an MR scan (study sequence is initiated), including subjects that have an incomplete scan. However, if a medically necessary scan occurs between implant and the MRI + 1 Month Visit, data for that subject will not be included in this endpoint.

[REDACTED]

The Kaplan-Meier methodology was chosen for this endpoint to utilize all available data for each subject. Subjects, who did not undergo an MR scan, i.e., the study sequence was not initiated, will be considered to have missing data. To assess the robustness of this analysis method and the potential impact missing data could have had on the analysis results, a tipping point analysis will be conducted that will include enrolled subjects. The tipping point analysis will assign each subject with missing data as either having or not having a MR Scan-related complication. All possible combinations of these patients' data will be evaluated along with the actual observed data to find the point, if any, at which the endpoint is failed.

13.1.2 Primary RV Effectiveness Endpoint 1: Pre-MR Scan vs. 1 Month Post-MR Scan RV Pacing Threshold at 0.5 ms

Increases in RV pacing threshold (at 0.5 ms) pre- MR scan and 1 Month post-MR scan will be calculated for subjects. Subjects that have an increase in average pacing thresholds $\leq 0.5V$ (at 0.5 ms) from pre-MR Scan to MRI Visit + 1 Month follow-up will be considered a success.

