11.2 Withdrawal

All subjects enrolled in the clinical study (including those withdrawn from the clinical study or lost to follow-up) shall be accounted for and documented. If a subject withdraws from the clinical investigation, the reason(s) shall be reported.

For US subjects: If such withdrawal is due to problems related to investigational device safety or performance, the investigator shall ask for the subject’s permission to follow his/her status/condition outside of the clinical study until the implanted investigational devices are approved by the FDA or the device is explanted.

Reasons for withdrawal include, but are not limited to:

- Subject who does not receive a Boston Scientific ImageReady MR Conditional Defibrillation System (no follow-up requirements)
- Subject who receive only a partial Boston Scientific ImageReady MR Conditional Defibrillation System (see section 11.3.4 for follow-up requirements)
- Subjects that have a PG or lead changeout that is not a Boston Scientific ImageReady MR Conditional Defibrillation System component (See Section 5)
- Subjects in Phase I who refuse to undergo the study require MR scan and are not willing to be rolled into Phase II
- Subjects already enrolled with previous protocol versions, who have not performed the MRI visit and who meet the updated exclusion criterion #5
- Subjects who fail the heart rhythm monitoring requirements at the MRI visit
- Physician discretion
- Subject choice to withdraw consent
- Lost to follow-up
- Death

While study withdrawal is discouraged, subjects may withdraw from the ENABLE MRI study and/or the VF Induction Sub-study at any time, with or without reason, and without prejudice to further treatment.

All applicable case report forms up to the point of subject withdrawal and a “Subject Status” form must be completed. Subjects who are “lost-to-follow-up” should have documented attempts to contact them prior to completion of the “Subject Status” form.

Additional study data may no longer be collected after the point at which a subject has been withdrawn from the study or withdraws his/her consent, for whatever reason. All open adverse events should be closed or documented as chronic. Data collected up to the point of subject withdrawal may be used.

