12.7.3.2 Heart Rhythm Monitoring after MRI protection mode programming

It is **required** that the heart rhythm be monitored by the site Principal Investigator or a sub-investigator for all subjects after programming MRI protection mode ON and prior to initiation of the MR Scan.

- Monitor the heart rhythm for at least 5 minutes using the monitoring equipment screen. Heart rate and any abnormal rhythms, including incidence of ectopy shall be documented.
 - In particular, look for signs of progressive AV nodal block over time, permanent or intermittent complete AV block, or trifascicular block (alternating bundle branch block or PR > 200 ms with LBBB or other bifascicular block) or a sinus pause > 2s during this time period. **Any** occurrence of these events will disqualify subjects from undergoing the MRI.
 - For such subjects, MRI protection mode must be turned OFF. These subjects should be withdrawn from the study.

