13.2.7 Assessment of Programming the MRI Protection Mode

In order to understand the use of the MRI Protection Mode, the following time durations will be summarized using descriptive statistics for both study-related MR scans and medically necessary MR scans:

- Duration of the PG in the MRI Protection Mode
- Time from the start of the MRI Protection Mode to the start of the MR scan
- Time from the end of the MR scan to exiting the MRI Protection Mode

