21.1 Events Reportable by Sites to Sponsor

The Principal Investigator is responsible for determining the reportability of events. Reportable events include the following:

- All Device Related Adverse Events

- All Cardiac Events Related Adverse Events associated with an untoward medical occurrence
 - Pre-existing cardiac conditions are not considered reportable unless the condition has exacerbated
- All Study Procedure Related Adverse Events
- All MRI Scan Related Adverse Events, for both protocol required MR scans and medically necessary scans
- All Adverse Events Related to the use of the MRI Protection Mode
- All Serious Adverse Events (including death), regardless of causality
 - Planned hospitalizations for pre-existing conditions prior to enrolment are not considered a serious adverse event
 - Procedures required by the clinical investigational plan without serious deterioration in health are not considered a serious adverse event
 - For centers in Austria cancer must always be reported as a Serious Adverse Event
- All Device Deficiencies
- Unanticipated Adverse Device Effects/Unanticipated Serious Adverse Device Effects previously not defined in the physician manuals

If it is unclear whether or not an event fits one of the above categories, or if the event cannot be isolated from the device, it should be submitted as an adverse event and/or device deficiency.

Events reported to Boston Scientific during the study will be reviewed and reported to comply with applicable regulations (relevant parts of ISO 14155: 2011 and/or 21 CFR Part 812). Investigators will be asked to classify whether an adverse event is considered serious or non-serious, whether it is anticipated or unanticipated (meets USADE/ UADE definition) as defined in Table 21-1 below, and whether it is considered device or procedure related, as defined in section 21.4.2. Any event that is determined to be an unanticipated serious adverse device effect (USADE; ISO 14155: 2011) will also be considered an unanticipated adverse device effect (UADE; CFR Part 812), as defined in Table 21-1 below.

Death should not be recorded as an adverse event. Death should be recorded as an outcome of only one (1) serious adverse event.

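### The primary safety analysis starts at the first scan sequence, so a complication seen earlier in MRI Protection Mode in a subject who is then not scanned is treated as missing

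*Combined protocol and SAP*

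**What the plan says.** Two passages fix the population. Section 13.1.1 states that "The primary safety endpoint will be assessed for all subjects who undergo any portion of the study-required MR scan sequences". Section 13.1.1.3 states that "Endpoint analysis will be performed on all subjects that undergo an MR scan (study sequence is initiated", and it keeps subjects whose scan was started but not finished. The measure in section 13.1.1 is the "Complication-free rate (CFR) between the MR Scan and the MRI Visit + 1 Month". The hypotheses in 13.1.1.1 use the same start, against a goal of 90%. Under 13.1.1.3 a subject with no sequence started has missing data. A tipping-point analysis that includes enrolled subjects then sets each missing outcome both ways.

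Section 5.1.1 says that Protection Mode suspends pacing, resynchronization and tachycardia detection and therapy. Section 12.7.3.2 requires at least 5 minutes of rhythm monitoring after the mode is on and before the scan. Listed AV-block and trifascicular-block findings, or a sinus pause above 2 s, bar the scan: "For such subjects, MRI protection mode must be turned OFF. These subjects should be withdrawn from the study". Section 11.2 adds: "Additional study data may no longer be collected after the point at which a subject has been withdrawn from the study".

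Three other places bear on the point. Section 21.1 makes reportable "All Adverse Events Related to the use of the MRI Protection Mode". Section 23.1 has the Clinical Events Committee review events related to the study scan and the system "between the MRI Visit and MRI + 1 month Visit (safety endpoint". Section 13.2.7 summarises "Time from the start of the MRI Protection Mode to the start of the MR scan" and two other durations, but no harm.

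**The concern.** The objective in section 7 is the safety of the system in the 1.5T environment under its labeled Conditions of Use. Section 6.1 makes Protection Mode during the scan one of those conditions, so the mode is part of what is being tested. Entry to the primary safety set nevertheless depends on what happens during the first minutes of exposure to it. If harm in those minutes stops the scan, the subject leaves the set and the observed outcome is not used.

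At stake is whether the trial can report on the system as it is used, from the moment therapy is suspended. Section 20.3 states that the mode adds no risk, while section 20.4 lists bradycardia, syncope and death as possible even when the Conditions of Use are met. A reader of the study report would want the observed events from programming onward, and no visible analysis supplies them.

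**Working it through.** The plan gives no figure to reproduce. The safety sample size (13.1.1.2) and the matching cells of the synopsis table are redacted. The check is therefore a reading of the rules, followed by algebra on direction.

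**Step 1. Where each kind of subject goes after Protection Mode is programmed.**

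| Subject | In the primary safety set? | Outcome used |
|---|---|---|
| Scanned; complication after the first sequence | Yes | Observed, if adjudicated as scan-related |
| Scanned; complication before the first sequence | Yes | Unclear: outside the window in 13.1.1, inside the window in 23.1 |
| Not scanned; complication in Protection Mode | No | Missing; set both ways in the tipping-point analysis |
| Not scanned; no complication | No | Missing; set both ways in the tipping-point analysis |

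The last two rows are treated alike although their outcomes were observed and differ.

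**Step 2. Does another route bring the third row back?** Under 13.1.1 the committee adjudicates complications that the site reports as related to the scan and the system. A subject with no scan has no scan-related event to report. Section 23.1 adds all deaths, and other events only at the sponsor's discretion. A non-fatal Protection Mode complication in an unscanned subject is thus recorded as an adverse event, but it is not assured adjudication and has no planned summary.

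**Step 3. Direction.** Ignore censoring. Let n be the number scanned and c the complications counted among them. Let u be the number programmed, not scanned and free of complications, and m the number programmed, not scanned and with a complication. Let k be the number scanned whose only complication came before the first sequence.

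- Current rate: 1 − c/n.
- Rate from programming: 1 − (c + m + k)/(n + u + m).

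With k = 0, the second rate is lower exactly when n(c + m) > c(n + u + m), that is, when m/(u + m) > c/n. If m = k = 0, the second rate is equal or slightly higher, because disqualified subjects without harm enter as successes. The difference depends on m, u and k, and the documents give none of them.

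**Step 4. Room against the goal (N assumed).** Take an exact one-sided binomial test against 90% at 2.5%, the level in 13.4.2, as a no-censoring stand-in for the Kaplan-Meier analysis. The largest number of complications that still passes is:

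| Assumed N | 100 | 150 | 200 | 250 | 300 |
|---|---|---|---|---|---|
| Complications allowed | 4 | 7 | 11 | 15 | 19 |

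A few extra events change the conclusion only if the count among scanned subjects is already at or near its limit.

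**The case against.** The strongest reply is that the endpoint is named and defined as scan-related, so starting at the scan matches its label. Counting from programming answers a different question. This stands, and it is why the primary endpoint should stay as it is.

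Several further points also stand.

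- **Tipping point.** It includes the worst case, with every unscanned subject set as a complication. It still does not use what was observed.
- **Recording.** Section 21.1 covers Protection Mode events and all serious adverse events. Section 11.2 requires case report forms up to withdrawal, asks that open adverse events be closed or documented as chronic, and allows data up to withdrawal to be used. It also asks certain US subjects for permission to be followed. A reader might infer that this harm goes unrecorded; the documents do not support that.
- **Definition.** Table 21-2 requires death, serious injury, invasive correction or permanent loss of device function. A reader might count every disqualified subject as a lost safety event. A pause above 2 s or trifascicular block is not one unless it leads to such an outcome.
- **Arrhythmia.** A reader might assume that any untreated tachyarrhythmia removes the subject by rule. The list in 12.7.3.2 names no ventricular tachyarrhythmia. Such a subject leaves the set only if the scan is not started.
- **Prior filter.** Section 12.7.2.3 requires at least 5 minutes at VVI 40 before the mode is programmed, and one paced beat disqualifies. Many subjects who rely on pacing are removed before the interval in question.
- **Conditions of Use.** Condition 5 in section 6.1 requires a patient judged able to tolerate no support throughout the mode. A subject who fails the check arguably no longer meets it.
- **Redaction.** A blacked-out paragraph in 13.1.1.3 may state the Kaplan-Meier time origin. The population rule and the hypotheses are visible and do not depend on it.

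**Conclusion.** The point holds in limited form. For a subject who has a complication in Protection Mode and is not scanned, the primary analysis discards an observed outcome, the sensitivity analysis replaces it with hypothetical ones, and no visible analysis reports it. Sections 13.1.1 and 13.1.1.1 also disagree with 23.1 on when the window opens.

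The size cannot be derived from the documents. Lost events are probably few, given Table 21-2 and the prior filter in 12.7.2.3, and the conclusion against 90% is unlikely to change. That is a judgement, not a calculation.

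Two stronger readings are tempting. One is that the reported rate materially overstates safety. Step 3 shows that even the direction depends on unknown counts. The other is that the type I error of the primary test is inflated. With a true rate from programming of exactly 90% and 2% of subjects dropped with a pre-scan complication, the stand-in test would pass with probability 3.7% (N = 100) to 16.9% (N = 300), against a nominal 2.5%. The 2%, the 90% and N are all assumptions, and the inflation is relative to an estimand that the plan does not claim to test. Neither reading is supported. This is a low-cost improvement and not a defect in the primary test.

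**What to change.** 1. Keep the scan-related primary endpoint and its test. Align 13.1.1, 13.1.1.1 and 23.1 on one window start.
2. Prespecify one supportive analysis of all subjects in whom Protection Mode is programmed for the study scan. Start the clock at programming. Count observed, committee-adjudicated complications related to the scan or to Protection Mode. Report how many were programmed but not scanned, and why.
3. In the tipping-point analysis, use the observed outcome of an unscanned subject where there is one, and vary only those that are truly unknown.
4. Reconcile 12.7.3.2 and 11.2, which withdraw these subjects and end data collection, with the safety follow-up given elsewhere. Section 11.3.3 follows Attempt subjects for 30 ± 7 days. Section 11.1.1 asks that already scanned subjects who meet updated exclusion criterion 5 not be withdrawn, if possible, before MRI + 1 Month. The aim is that adverse events in the few subjects disqualified in Protection Mode are captured. The disqualification rule itself is not in question.

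The cost is one extra table, a little more adjudication, a small protocol wording change that may need the approvals in section 15, and possibly a slightly less favourable supportive rate. Protection Mode adverse events are already reportable, and the durations in 13.2.7 already need the programming time.
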